MAGIC grade assessment	X	X	X	X	X	X	X	X	X	X	X	X	X
Questionnaires ¹⁵	X	X	X	X	X	X	X	X	X	X	X	X	X

ADA=anti-drug antibody; CR=complete response; CT=computed tomography; ECG=electrocardiogram; eCRF=electronic Case Report Form; EO²=end of trial; GI=gastrointestinal; MAGIC= Mount Sinai Acute Graft Versus Host Disease International Consortium; MR=magnetic resonance; PK=pharmacokinetics; NA=Not applicable

Footnotes to Table 2:

1. Follow-up visits:
 - If a complete lower GI-aGVHD response is achieved by Week 8 inclusive, follow-up visits at Weeks 8, 13, 17, 21, 26, 52, and 104 should be completed
 - If a complete lower GI-aGVHD response is achieved from Week 9 to Week 13 inclusive, follow-up visits at Weeks 13, 17, 21, 26, 52, and 104 should be completed
 - If a complete lower GI-aGVHD response is achieved during the optional treatment period or lower GI-aGVHD flare treatment, perform the next follow-up visit available after a complete lower GI-aGVHD response is achieved (for example, if a complete lower GI-aGVHD response is achieved at Week 20, perform follow-up visits at Weeks 21, 26, 52, and 104)
2. In case of early treatment discontinuation, an early treatment discontinuation visit should be performed at approximately 4 weeks (+1 week) after the last IMP dose. Follow-up starts from the early treatment discontinuation visit and the subject will then transition to Weeks 26, 52, and 104 (EOT)
3. In case of early trial discontinuation, the subject will be asked to return to the site approximately 4 weeks (+1 week) from the date of early trial discontinuation. After this visit, there will be no further visits
4. All visit procedures are recommended to be done on the same day, unless otherwise specified
5. In Germany, only colonoscopy or MR enterography will be performed (not CT colonography)
6. The Day 56 lower GI biopsy is optional and should be done only if a lower GI biopsy was done prior to apaglutide therapy and if the subject is medically suitable for the procedure
7. Vital signs (blood pressure, heart rate, temperature)
8. A phone call must be performed every 4 weeks (\pm 72 hours) between Weeks 26 and 104 to collect information regarding adverse events, concomitant medications, weight changes, and other pertinent information to assess the subject's medical condition. Phone calls will not be undertaken when the subject is attending the site for a scheduled visit

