2.2.3 Follow-up Period

The follow-up period will last up approximately 2 years from the first investigational medicinal product (IMP) administration and will start at different time points during the trial:

- If a complete lower GI-aGVHD response is achieved by Week 8 inclusive, the subject will transition to follow-up at Week 8. Follow-up visits at Weeks 8, 13, 17, 21, 26, 52, and 104/EOT should be performed
- If a complete lower GI-aGVHD response is achieved from Week 9 to Week 13 inclusive, the subject will transition to follow-up at Week 13. Follow-up visits at Weeks 13, 17, 21, 26, 52, and 104/EOT should be performed
- If a complete lower GI-aGVHD response is achieved during the optional treatment or lower GI-aGVHD flare treatment, the subject will transition to follow-up. E.g., if a complete lower GI-aGVHD response is achieved at Week 20, only the visits at Weeks 21, 26, 52, and 104/EOT should be performed
- In case of early treatment discontinuation, the subject will attend an early treatment discontinuation visit approximately 4 weeks (+1 week) from the last IMP dose and subsequently transition to follow-up visits at Weeks 26, 52, and 104/EOT

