2.2.4 Phone Calls

Between Week 26 and Week 104/EOT, the site will contact the subject approximately every 4 weeks via telephone. Phone calls will not be made in the same week that a trial visit is scheduled. Unscheduled calls can be performed at the discretion of the Investigator.

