2.2.6 Early Treatment Discontinuation

A subject who discontinues treatment early is NOT considered to be withdrawn from the trial, but rather the subject will be followed up until the planned Week 104/EOT visit, provided that the subject's consent has not been withdrawn.

An early treatment discontinuation visit should be scheduled approximately 4 weeks (+1 week) from the last IMP dose. The subject will then transition to follow-up visits at Weeks 26, 52, and 104/EOT. The same visit should be completed also in case of early treatment discontinuation during the optional treatment period.

The decision for early treatment discontinuation can be made by the subject, the Investigator, or Sponsor personnel. A subject has the right to prematurely discontinue

trial medication at any time, without any justification, by withdrawal from trial medication only or by withdrawal from any further participation in the trial (i.e., early trial discontinuation [see Section 2.2.7]).

Although a subject is not obliged to give his/her reason for prematurely withdrawing from the treatment or the trial, it is recommended that the Investigator makes a reasonable effort to ascertain the reason(s), while fully respecting the subject's rights.

The Investigator must discontinue trial medication for a given subject if, on balance, he/she believes that continued administration would be contrary to the best interests of the subject.

A subject who discontinues treatment early and withdraws consent to participate in any further trial assessments is considered as withdrawn from the trial and no further assessment will be collected after informed consent withdrawal.

Apaglutide should be permanently stopped under the following conditions:

- New malignancy is identified during the trial (subjects must be treated and followed up as per local guidelines and practices for those malignancies)
- In case of an elevation of laboratory parameters as reported in Table 6
- The subject is pregnant
- In case of unacceptable toxicities associated (definitely, probably, possibly related) with apaglutide

For further considerations on IMP dose reduction and temporary discontinuation, see Section 6.6.2.

The Investigator must discontinue trial medication for a given subject if, on balance, he/she believes that continued administration would be contrary to the best interests of the subject.

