## 1 INTRODUCTION

This Statistical Analysis Plan (SAP) for Final Analysis (FA) describes the procedures and timeline for the Final Analysis specified in the protocol TA799-101 5.0, FINAL, 27/MAR/2023 ([VectivBio AG 2023](#)). For the rationale and aim of the trial, please refer to the *protocol* for details. The Final analysis will be done in two steps. The Primary analysis of safety and efficacy will be performed once all subjects have either completed Day 91 or withdrawn from the trial. Additional analyses will be done once all the subjects have either completed the end of trial (EOT) visit or withdrawn from the trial. This additional analysis will be referred to as “EOT analysis”.

The Primary Analysis targets the characterization of the safety profile and the obtention of efficacy results. It will be used to support the Clinical Trial Report (CTR). The EOT analysis will feed an addendum to the CTR that will cover the follow-up period until 2 years after the first apaglutide dose.

All decisions regarding Primary analysis, as defined in the present SAP document, have been made prior to database snapshot for the Primary analysis. This SAP FA consists of an extension of the SAP of the Interim Analysis (IA) performed for this trial.

The clinical cut-off date for the Primary analysis will be when all enrolled subjects have either reached Day 91 or withdrawn from trial: up to 01 Dec 2023 (included). All available data points by the clinical cut-off date will be included in the Primary analysis; at the time of the data extract, all data points after the clinical cut-off date will be programmatically cut. Data extracted from the electronic data capture (EDC) system and data transferred from external vendor sources (e.g., lab data) will be mapped into the Study Data Tabulation Model (SDTM, v1.7 and implementation guidelines SDTMIG 3.3) datasets which will be used as the source data for the Primary analysis. Note that the technical procedures and steps for processing these data and for implementing the definitions of variables for the purpose of the statistical analysis are covered in the analysis datasets specifications document (programming cut-off, analysis data model, ADaM, v2.1 and implementation guidelines ADaMIG 1.2).

The Final Analysis will be performed under single-blind design of the trial. Actual treatments will be mapped into the SDTM. Details of the unblinding procedure are described in the Trial Blinding Plan.

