#### *4.3.9.11 Incidence of malignancy relapse up to 2 years post-first dose of apaglutide*

The malignancy relapse/progression time is defined as the time from the date of the first dose to the date of hematologic malignancy relapse/progression.

Hematologic malignancy relapse/progression will be identified by manual review of reported malignancies or relapses in the AE data against the Underlying disease history CRF by the medical team, and confirmed with Sponsor. The list of identified hematologic malignancy relapse/progression will be finalized prior to the data base lock both for the Primary and the EOT analysis.

The malignancy/relapse progression will be summarized using Kaplan-Meier estimator. The number and percentage of subjects experiencing an event, and subjects censored will be summarized by apaglutide dose levels and in total. The median time-to-event will be presented where possible, along with the range and the associated two-sided 95% Brookmeyer-Crowley confidence interval. The event-free rate with 95% CI using Greenwood's formula will be provided for selected time points (e.g., 1, 3, 6, 12 and 24 months).

Plots of the Kaplan-Meier estimate for the malignancy/relapse progression will be presented by apaglutide dose levels and in total.

Subject for which no malignancy/relapse progression event occurs will be right censored at their last follow-up visit.

Incidence of malignancy/relapse progression will be analyzed only for the EOT analysis.

*4.3.9.12 Overall Survival up to 2 years post-first dose of apaglutide*

The overall survival time is defined as the time from the date of the first dose to the date of death due to any cause.

The last date known to be alive for each individual subject may be determined using, but not limited to, the following dates recorded on the eCRF:

- AE start and stop dates
- Study treatment start and stop dates
- Sample collection date for laboratory assessments
- Dates of any performed visit
- Start and stop dates of concomitant medications

Subjects who are alive at the time of data cut-off will be right censored on the date the subject was last known to be alive.

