The overall survival time will be summarized using Kaplan-Meier estimator. The number and percentage of subjects experiencing an event (death), and subjects censored will be summarized by apaglutide dose levels and in total. The median time-to-event will be presented where possible, along with the range and the associated two-sided 95% Brookmeyer-Crowley confidence interval.

Plots of the Kaplan-Meier estimate for the overall survival will be presented by apaglutide dose levels and in total.

Overall Survival will be analyzed only for the EOT analysis.

*4.3.9.13 Non-relapse Mortality up to 2 years post-first dose of apaglutide*

The non-relapse mortality time is defined as the time from the date of the first dose to the date of death not preceded by hematologic malignancy relapse/progression.

The non-relapse mortality will be summarized using Kaplan-Meier estimator. The number and percentage of subjects experiencing an event, and subjects censored will be summarized by apaglutide dose levels and in total. The median time-to-event will be presented where possible, along with the range and the associated two-sided 95% Brookmeyer-Crowley confidence interval. The event-free rate with 95% CI using Greenwood's formula will be provided for selected time points (e.g., 1, 3, 6, 12 and 24 months).

Plots of the Kaplan-Meier estimate for the non-relapse mortality will be presented by apraglutide dose levels and in total.

Subject for which “hematologic malignancy relapse/progression” event occurs will be right censored at the time of occurrence of the event.

Subject for which neither “death” or “hematologic malignancy relapse/progression” event occurs will be right censored at their last follow-up visit.

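### At the Primary Analysis, NRM and FFS censor event-free subjects at their last visit but count events found between visits, so Kaplan-Meier estimates beyond about six months overstate NRM and understate FFS.

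*SAP*

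**What the plan says.** **Censoring rule.** SAP 4.3.9.13 (NRM), 4.3.9.14 (FFS) and 4.3.9.9 (duration of response from Day 28 or Day 56 on total MAGIC) use the same wording: a subject for whom no "event occurs will be right censored at their last follow-up visit". For overall survival (OS), SAP 4.3.9.12 differs: subjects alive at cut-off "will be right censored on the date the subject was last known to be alive", a date that may come from AE, treatment, laboratory, visit or medication records.

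**Visits and calls.** Protocol 2.2.3 says, for a response reached by Week 13: "Follow-up visits at Weeks 13, 17, 21, 26, 52, and 104/EOT should be performed". After early treatment discontinuation there is one visit about 4 weeks after the last dose, and then, under Protocol 2.2.6, "The subject will then transition to follow-up visits at Weeks 26, 52, and 104/EOT". From Week 26 to Week 104, Protocol 2.2.4 says "the site will contact the subject approximately every 4 weeks via telephone". Footnote 8 to Protocol Table 2 adds "A phone call must be performed every 4 weeks", and says that the calls run "between Weeks 26 and 104 to collect information regarding adverse events, concomitant medications, weight changes".

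**What enters the analysis.** SAP section 1 states "All available data points by the clinical cut-off date will be included in the Primary analysis", and that endpoints are analysed at both steps unless otherwise specified. SAP 3.2 labels OS, relapse and graft failure as EOT only. NRM, FFS and duration of response carry no such label.

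**The concern.** Kaplan-Meier estimation requires that leaving the risk set is unrelated to the outcome. Here it is not. A death at Week 50 is an event at Week 50. A subject known from a call to be event-free at Week 50 is taken out of the risk set at Week 26. Follow-up is cut back only for those who did not have the event.

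Event information does not stop at visits. Deaths carry their own date, and Protocol 5.5 has sites trace survival status through the treating physician or next of kin when a subject fails to attend. Relapse is identified from AE data (SAP 4.3.9.11). New systemic therapy comes from the medication and procedure pages (SAP Appendix A). The calls feed both.

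The Primary Analysis supports the Clinical Trial Report. It presents NRM and FFS with Kaplan-Meier plots and event-free rates at selected times, 12 months being one of the examples. It leaves OS, which has the sounder rule, to the EOT analysis. No comparison with external data is planned at that step (SAP section 6, item 7), so these curves will be read as absolute rates.

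**Working it through.** The documents give no figure for NRM or FFS, so there is none to reproduce.

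**1. Follow-up that can be lost.** Between Week 26 and Week 52: 52 − 26 = 26 weeks, apart from visit windows. Between Week 52 and Week 104: 104 − 52 = 52 weeks, which can affect only estimates beyond 12 months. Counting calls as contacts reduces the loss to about 4 weeks.

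**2. Direction.** At an event time t between Weeks 26 and 52, let n subjects have known follow-up to at least t. Let c of these be event-free and known to be so at t, but not yet at their Week 52 visit. The Kaplan-Meier factors are

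- last contact: 1 − 1/n
- last visit (SAP): 1 − 1/(n − c)

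The second is smaller whenever c > 0, so NRM is overstated and FFS understated. In the limit where nobody has reached Week 52, the only subjects left at risk after Week 26 are those who go on to have an event, and the curve falls to zero at the last such event.

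**3. Size at the Primary Analysis.** From the documents: visits at Weeks 0-4, 6, 8, 13, 17, 21, 26, 52 and 104; calls every 4 weeks after Week 26; minimum follow-up of about 13 weeks, since every subject has reached Day 91 or withdrawn. Assumed: follow-up at cut-off uniform from 13 weeks to a stated maximum; Weibull event times with shape 1.0 (constant hazard) or 0.6 (early hazard); a true 12-month NRM. Sixty replicates of 2,000 subjects were used, to show bias rather than noise, with the estimate read just before Week 52. Ranges span the two shapes.

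| True 12-month NRM | Maximum follow-up | SAP rule | Last visit or call |
|---|---|---|---|
| 40% | 65 weeks | 49-52% | 41-42% |
| 40% | 78 weeks | 45-46% | 41% |
| 40% | 93 weeks | 43-44% | 41% |
| 30% | 65 weeks | 38-40% | 31% |
| 30% | 78 weeks | 34-36% | 31% |
| 30% | 93 weeks | 33-34% | 31% |

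With censoring at the cut-off itself, the estimates return 40% and 30%. Event-free subjects lose about 8 to 14 weeks on average. The six-month estimate moves by at most 0.5 points (for example 22.3% to 22.8%).

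**4. At the trial's size (N = 34).** With a true 12-month event-free rate of 0.50 and shape 0.7:

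| Follow-up | Cut-off | SAP rule | Last contact | SAP − cut-off |
|---|---|---|---|---|
| 13-87 weeks | 0.499 | 0.454 | 0.490 | −0.045 |
| 13-60 weeks | 0.499 | 0.353 | 0.478 | −0.146 |

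Across true rates of 0.3, 0.5 and 0.7 and shapes 0.5 to 1.0, the fall is 3-5 points for 13-87 weeks and 10-17 points for 13-60 weeks.

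**5. EOT analysis.** With complete 104-week follow-up the two rules agree. With 10-20% dropout (shape 0.7), the largest differences are 0.502 − 0.498 = 0.4 points at 12 months and 0.324 − 0.314 = 1.0 point at 24 months.

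The simulations gave every subject the full visit schedule. The sparser schedule after early treatment discontinuation was not modelled.

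**The case against.** **Noise exceeds bias.** With 34 subjects and a true NRM of 40%, the standard deviation of the 12-month estimate is about 9-11 points even with censoring at cut-off, with about 5-10 subjects at risk at Week 52. Per arm of 15 it is about 14-17 points. The results are descriptive and no decision rule uses them. This stands as a limit on importance. It does not remove the bias, which runs one way and is not reflected in the Greenwood intervals.

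**The 12-month landmark is only an example.** The listed times are introduced as examples, so the SAP does not compel a 12-month figure from immature data. True, but the curve and plot beyond Week 26 are produced all the same.

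**Calls may count as visits.** Protocol Table 2 lists the call among the follow-up visits, and the dataset specification, which is a separate document, may define the date. On that reading the residual bias is about 0.5-3 points. But Protocol 2.2.4 keeps calls and visits apart by avoiding calls in visit weeks, and the SAP does not mention calls in its censoring rules.

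**Stronger readings that the documents do not support.**

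- A reader might infer that the 2-year results are equally biased. Subjects who leave the trial are asked back about 4 weeks later, and the EOT effect is about 1 point or less.
- A reader might apply the 52-week gap to the 12-month estimate. That gap begins at Week 52, so it cannot.
- A reader might assume that most subjects are between visits at cut-off. The documents do not give accrual dates, and up to Week 26 scheduled visits are at most about 5 weeks apart for subjects who have not stopped treatment early.

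**Conclusion.** The censoring rule for NRM and FFS is wrong as written for the Primary Analysis. Whether an event-free subject's time after the last visit is kept depends on the outcome, and the direction is fixed: NRM too high and FFS too low after about six months. Under the assumed accrual and a true 12-month NRM of 40%, the excess is roughly 3 to 12 points (43-52%), against at most about 2 points with last-contact censoring. It would be larger if few subjects had reached Week 52 by 01 Dec 2023, and smaller if many had. These sizes depend on accrual and event rates that the documents do not give; the direction does not. Estimates up to six months and the EOT analysis are essentially unaffected. The rule should be corrected, but it does not undermine the trial.

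**What to change.** In SAP 4.3.9.13 and 4.3.9.14, and in 4.3.9.9, which has the same rule and is also run at the Primary Analysis, censor event-free subjects at the last contact on or before the clinical cut-off at which that endpoint's event status was ascertained. Such a contact is a visit, or a completed phone call with review of adverse events and concomitant medication. Name phone-call dates as a source.

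Do not simply reuse the OS last-known-alive variable for FFS or response duration. A laboratory date or an AE stop date shows that a subject was alive, not that relapse or new systemic therapy had been ruled out. Aligning relapse (4.3.9.11), which is analysed only at EOT, is for consistency.

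The cost is SAP wording, an event-specific last-contact date in the analysis datasets, and, if the change follows sign-off of SAP version 2.0, a documented amendment. The calls are already required by the protocol, so no new data are needed.

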#### *4.3.9.14 Failure-free survival up to 2 years post-first dose of apraglutide*

The failure-free survival time is defined as the time from the date of the first dose to the date of hematologic malignancy relapse/progression, non-relapse mortality, or the start of additional systemic therapy for GI-aGVHD, whichever occurs first.

The failure-free survival will be summarized using Kaplan-Meier estimator. The number and percentage of subjects experiencing an event, and subjects censored will be summarized by apraglutide dose levels and in total. The median time-to-event will be presented where possible, along with the range and the associated two-sided 95% Brookmeyer-Crowley confidence interval. The event-free rate with 95% CI using Greenwood’s formula will be provided for selected time points (e.g., 1, 3, 6, 12 and 24 months).

Subject for which neither “new systemic therapy for aGVHD”, “hematologic malignancy relapse/progression” or “non-relapse mortality” event occurs will be right censored at their last follow-up visit.

Plots of the Kaplan-Meier estimate for the failure-free survival will be presented by apraglutide dose levels and in total.

